4.3.4.1 Screening Interview

The screening interview (see Attachment 4, Recruitment Script) involves educating patients about the study and obtaining their verbal permission to conduct screening activities (under waiver of documentation of consent). Interview questions pertain to eligibility criteria, anxiety and cognitive screens.

Anxiety: The GAS-10 is a 10-item instrument that measures anxiety symptoms in adults/older adults; items were derived from the range of anxiety disorder symptoms in the DSM-IV-TR.^{148,149} The GAS-10 will be administered to patients to minimize variance for the purposes of a pilot study. Per the expert recommendation of collaborators who administer the rtACS intervention, the basis for including this test as part of the screening process is that said collaborators have found that people with greater anxiety have a poorer response to rtACS. The GAS-10 will be administered per protocol. Patients who score ≥ 12 are excluded from the study based on receiver operating characteristic analyses. Eligibility for enrollment in the study based on the GAS-10 score will be indicated on the Recruitment Script form.

Cognition: The TICS-m is a 13-item instrument that will be administered as part of the screening process to identify potential patients with a cognitive impairment who are likely unable to accurately complete self-report questionnaires.^{150,151} The TICS-m can be administered either face-to-face or via the telephone, which is why it is the tool chosen for the screening process. The TICS-m will be administered per protocol. Patients who score ≤ 27 are excluded from the study; based on score interpretation that these people have greater than mild cognitive impairment.¹⁵² Eligibility for enrollment in the study based on the TICS-m score will be indicated on the Recruitment Script form.

- **Setup:** The GAS-10 and TICS-m will be administered in a distraction free room. When administered via the telephone, patients will be prompted that they should be in a distraction free area and should not be interrupted during the interview.

CONFIDENTIAL

This material is the property of the NYU School of Medicine and Langone Medical Center. Do not disclose or use except as authorized in writing by the study sponsor

4.3.4.2 Medical Record Review

A review of patients' ophthalmic medical records will be conducted as part of the screening process to ensure there were no significant changes identified during their ophthalmic examination to determine patients' eligibility for this pilot study (see Attachment 4, Screening Form). Eligibility for enrollment in the study based on the medical record review will be indicated on the Screening Form. Patient identifiable information will only be recorded from the medical record after patients enroll in the study.

Procedure: Screening

- When trained research personnel are present at the Centers, screening procedures will be conducted the same day as the clinical appointment per patient's availability.
 - Research personnel will be present as often possible at the Centers on those days when the physicians involved in this study are scheduled with clinical appointments.
 - Screening procedures will be conducted in a private room, distraction free, to safeguard privacy.
- When trained research personnel are not available to conduct screening activities, the patient's verbal permission that his/her information can be shared with the research team will be obtained and documented and the patient will be informed that a trained research team member will contact him/her to discuss the research study and screening procedures. The research personnel's contact information will be provided to the patient so he/she is aware of whom to expect will be contacting him/her.
 - Patients will be contacted via phone unless otherwise specified by the patient at the time when verbal permission was obtained and documented.
 - Research personnel will contact patients within two business days of being informed of the patient's permission that his/her information can be shared with the research team. Three attempts will be made within 7 days. After three attempts, research personnel will initiate no further phone contact.
- When patients are not able or available to participate in screening activities the same day as their clinical visit, screening procedures will follow those described for when trained research personnel are not available.
- Once all screening procedures are completed and the information analyzed, patients will be informed of their eligibility to participate in this study.
 - Patients will be informed of their eligibility to participate in the study as soon as possible, no more than two business days following completion of screening procedures. This timeframe is established to account for potential variability in the timing of the screening procedures, patients' availability, and documentation of medical record review.
- For those patients who meet the eligibility criteria and agree to participate in the study, trained research personnel will schedule a date and time to meet with the patient to review and obtain written informed consent prior to initiating administration of study assessments (see Attachment 4, Participant Visit Schedule).

In the case when NYU Langone Eye Center/a member of the research team is contacted by an entity other than an NYU Langone Health patient in regard to rtACS research, the screening interview will be conducted via phone. A health records review will be conducted again to confirm no conflicting reports between information gathered during the screening interview with what is documented in the entity's health records. All other screening procedures are the same as conducted for the Centers.

CONFIDENTIAL

This material is the property of the NYU School of Medicine and Langone Medical Center. Do not disclose or use except as authorized in writing by the study sponsor

4.4 Early Withdrawal of Subjects

4.4.1 When and How to Withdraw Subjects

Research personnel will monitor participants throughout the course of the study. Participants may be withdrawn from the study as decided by trained research personnel prior to the expected completion of that participant's role in the study. Reasons for withdrawal may include, but not be limited to:

- Adverse event
- Change in status relevant for inclusion or exclusion eligibility
- Change in medical diagnosis or treatment
- Non-compliance with study protocol
- Atypical skin condition*
- Atypical headache**
- Atypical discomfort***

*Erythema (skin reddening) is not a criterion for withdrawal. It is an anticipated effect (monitored) that may occur following the intervention as a result of increased blood flow at the site of the electrodes due to vasodilation as a secondary effect of current application across the skin and tissue barriers.

**Headaches naturally occur in the normal population. Atypical headache is an unusual headache either in occurrence or in intensity.

***Atypical discomfort entails an event when a participant expresses a desire to terminate a session, i.e., electrical stimulation would be aborted. In this case, when a participant requests to terminate a session, they will be withdrawn from the study.

Because the risk profile of ACS is very low, no research-related injury is anticipated. The delivered current is weak, such that it can hardly be felt. In the unlikely event that a participant reports clinically-relevant harm from the study, this information will be conveyed to the study physician who will evaluate the participant. The physician will ensure that the participant has appropriate medical follow-up when indicated. If the event is serious and unexpected, the event will be reported to the IRB, per their reporting guidelines.

4.4.2 Data Collection and Follow-up for Withdrawn Subjects

In the case when a participant is withdrawn from the study, prior to the expected completion of that participant's role in the study as decided by trained research personnel, we will obtain written permission to collect relevant follow-up data that directly pertains to the safety of that participant in regard to the intervention (e.g., adverse event/adverse effect related to intervention). Participants may withdraw their consent to participate in the study at any time. Any identifiable research or medical information recorded for or resulting from the participant's participation in the study prior to the date that the participant formally withdrew consent (written notification of withdrawal) may be used and disclosed by the investigators for the purposes of the study described above.

5 Study Device

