5.4 Subject Compliance Monitoring

Research personnel will monitor and document participants' compliance with attendance at scheduled baseline assessments, daily intervention sessions, and follow-up assessments. As part of the recruitment process, patients will be interviewed in regard to their availability to attend 10 daily sessions over a 2-week period. Participants' baseline assessments will be scheduled to accommodate their schedule within reason and the timeframe for the conduct of this study. In the event when an enrolled participant is unable to adhere to the study protocol, consideration for withdrawal will be discussed and documented by the research team.

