6.3 Visit: Post-intervention

Post-intervention assessments will be scheduled for administration within five business days of participants' last intervention sessions.

Ophthalmic examination: Procedures follow standard practice including examination by an ophthalmologist and testing includes: recording medical and family history, VA testing, axial length, IOP and central corneal thickness measurements, slit lamp examination, indirect ophthalmoscopy, and stereophotography of the optic nerve head, macula, and nerve fiber layer. The total time requirement for the ophthalmic examination is approximately 45 minutes.

The following assessments (approximate minutes to complete) will be administered: Pre-/Post-session Questionnaire (5), VF (20), VA (5), CS (5), OCT (10), OCT-A (10), VEP and PERG (15), Verbal Fluency Test (5), Digit Span (5), LIFE-H (30), MNRead (10), VFQ-39 (25), SF-36 (25), and Post-intervention Interview (60).

The total time requirement for participants for post-intervention testing is 3 hours in addition to the ophthalmic evaluation.

CONFIDENTIAL

This material is the property of the NYU School of Medicine and Langone Medical Center. Do not disclose or use except as authorized in writing by the study sponsor

MRI testing will be performed at post-intervention and will require up to 2 hours. Post-intervention assessments may be scheduled on separate days due to timing, location of MRI facility, and patient scheduling.

The Brief COPE questionnaire (Attachment 10) will be included in the battery of questionnaires. The Brief COPE is a 28-item questionnaire designed to measure effective/ineffective coping in response to a stressful life event. The time requirement for the questionnaire is less than 5 minutes.

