6.4 Visit: Follow-up

Follow-up assessments will be scheduled for administration 4 weeks following the participants' last intervention sessions.

Ophthalmic examination: Procedures follow standard practice including examination by an ophthalmologist and testing includes: recording medical and family history, VA testing, axial length, IOP and central corneal thickness measurements, slit lamp examination, indirect ophthalmoscopy, and stereophotography of the optic nerve head, macula, and nerve fiber layer. The total time requirement for the ophthalmic examination is approximately 45 minutes.

The following assessments (approximate minutes to complete) will be administered: Pre-/Post-session Questionnaire (5), VF (20), VA (5), CS (5), OCT (10), OCT-A (10), VEP and PERG (15), Verbal Fluency Test (5), Digit Span (5), LIFE-H (30), MNRead (10), VFQ-39 (25), and SF-36 (25).

The total time requirement for participants for follow-up testing is approximately 3 hours in addition to the ophthalmic examination.

MRI testing will be performed at follow-up and will require up to 2 hours. Follow-up assessments may be scheduled on separate days due to timing, location of MRI facility, and patient scheduling.

The Brief COPE questionnaire (Attachment 10) will be included in the battery of questionnaires. The Brief COPE is a 28-item questionnaire designed to measure effective/ineffective coping in response to a stressful life event. The time requirement for the questionnaire is less than 5 minutes.

7 Statistical Plan

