7.1 Sample Size Determination

Given the objectives of this pilot study (see section 2) and limited data about the effect of rtACS for people with glaucoma, we estimate to enroll 16 participants to complete the study protocol. Our rationale for this number includes the following considerations: feasibility, quantifying an estimate of effect and estimate of variance, and validating methodologies.¹⁵³ We are using a block randomization scheme with a 1:1 allocation ratio for rtACS versus sham stimulation groups to collect data to inform the characterization of each group. We anticipate finding little to no effects in the sham stimulation group for a control but we establish equal allocation to groups to assess potential placebo effect.

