7.2 Statistical Methods

All study participants will be included in efficacy analyses as randomized (intent to treat population). Treatment effects on all outcomes will be estimated with 95% confidence interval. Supportive analyses will include estimating effects in study participants who received at least five sessions of their randomized assigned treatment as supportive analyses and hypothesis testing with two-sided tests at significance level of 0.05.

The primary outcome variables that will be evaluated in this study are structure and function of the retina and visual pathway (using imaging and electrophysiological technology), visual function, functional ability,

CONFIDENTIAL

This material is the property of the NYU School of Medicine and Langone Medical Center. Do not disclose or use except as authorized in writing by the study sponsor

and QoL. Secondary outcome variables include feasibility of procedures and methodologies for recruitment, enrollment, data collection and data management.

Subjective demographic and clinical characteristics will be analyzed using descriptive statistics. Continuous variables will be described by means and standard deviations (or by median and interquartile range for skew distribution) and categorical variables will be described by frequencies (count) and percentages. Overall, to analyze our aims and test our hypotheses we will use between and within group comparison analyses (e.g., *t*-tests) to evaluate change scores from baseline to post-intervention and follow-up between rtACS and sham stimulation groups. We will use effect size calculations to evaluate the magnitude of differences between and within groups. Additionally, we will quantify an estimate of variance using 95% confidence interval. Analyses will be conducted using R statistical computing software.

Aim 1 (2.1.1.1): Measure structural and functional capabilities of neuronal physiology and reorganization of the visual pathway (from eye to visual brain)

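### Participants withdrawn during the sessions have only safety follow-up planned, so in practice the promised intention-to-treat analysis would leave them out

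*Combined protocol and SAP*

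**What the plan says.** **Withdrawal.** Section 4.4.1 states "Participants may be withdrawn from the study as decided by trained research personnel" and lists reasons that include adverse events, non-compliance and atypical skin condition, headache or discomfort. One trigger is automatic: "when a participant requests to terminate a session, they will be withdrawn from the study". Missed sessions are treated more loosely in section 5.4, where "consideration for withdrawal will be discussed and documented by the research team".

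**Data after withdrawal.** For participants withdrawn by staff, section 4.4.2 says "we will obtain written permission to collect relevant follow-up data that directly pertains to the safety of that participant in regard to the intervention". For those who withdraw consent, it allows use of what was recorded up to that date.

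**Outcome visits.** Section 6.3 says "Post-intervention assessments will be scheduled for administration within five business days of" the last session, and section 6.4 says "Follow-up assessments will be scheduled for administration 4 weeks following the" last session. The session visits (6.2) collect only the Pre-/Post-session Questionnaire, which section 3.3.1.3 describes as vital signs, skin observation, therapy changes and symptoms.

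**Analysis.** Section 7.2 says "All study participants will be included in efficacy analyses as randomized (intent to treat population", and section 7.3 repeats that everyone randomised is analysed. The analysis variable is change from baseline. Section 7 has no imputation rule, likelihood-based model or sensitivity analysis for a missing outcome. Section 9.3 asks only that missing entries on the case report form be explained.

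**Sample size and recruitment.** The reasons given in 7.1 for 16 participants include "quantifying an estimate of effect and estimate of variance". Sections 4 and 4.3.1 continue recruitment until the planned intervention-group participants have completed follow-up.

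**The concern.** The withdrawal rules and the analysis population do not fit together. Section 4.4.1 treats stopping sessions as leaving the study, and 4.4.2 then plans no efficacy measurement. Sections 7.2 and 7.3 nevertheless promise to analyse everyone randomised. Following both sets of rules leads to a completer analysis under an intention-to-treat label.

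Some of the listed reasons for withdrawal (adverse event, skin condition, headache, discomfort) could relate to treatment, so the missing outcomes cannot be presumed random. The stake is the estimates of effect and variance that this pilot is meant to hand to a larger trial. With about 8 per arm, one person is 12.5% of an arm.

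**Working it through.** **1. The plan's own figure.** The sample size is 16, allocated 1:1, so 8 per arm if exactly balanced. Section 7.1 gives no effect size, SD, power or dropout rate, so there is nothing to reproduce.

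**2. Who ends up without a change score.**

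| Participant | Outcome visits still planned | Change score |
|---|---|---|
| Asks to end a session, so is withdrawn (4.4.1) | None; safety data only (4.4.2) | None |
| Withdrawn by staff during the sessions for another 4.4.1 reason | None; safety data only (4.4.2) | None |
| Withdraws consent during the sessions | None; earlier data usable (4.4.2) | None |
| Misses sessions but is not withdrawn (5.4) | Both | Both |
| Withdrawn after the post-intervention visit | First visit already done | Post-intervention only |

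The first three rows are the gap. The supportive analysis in 7.2 shares it: someone withdrawn after session 5 meets the five-session condition but has no outcome.

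**3. Possible shift in an arm's mean.** Let the gap be the withdrawn person's unobserved change minus the completers' mean change in the same arm, in SD units. Leaving out 1 of n randomised shifts the arm mean by gap/n. The documents give no gap; 0.5 to 1.5 SD is an assumption.

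- Loss not replaced, n = 8: 0.5/8 = 0.0625 and 1.5/8 = 0.1875, so 0.06 to 0.19 SD.
- Loss replaced, n = 9 randomised and 8 completing: 0.5/9 = 0.056 and 1.5/9 = 0.167, so 0.06 to 0.17 SD.
- A gap of 0 gives no shift. With one unreplaced loss in each arm and equal gaps, the shifts cancel in the between-arm difference.

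**4. Precision.** The 95% CI half-width for the between-arm difference, in SD units, is t(0.975, n1+n2−2) × √(1/n1 + 1/n2).

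- 8 v 8: 2.145 × √(1/8 + 1/8) = 1.07 SD
- 7 v 8: 2.160 × √(1/7 + 1/8) = 1.12 SD

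The second figure applies only to an unreplaced loss. The largest shift in step 3 is 0.1875/1.072 = 17% of the 8 v 8 half-width, and the smallest unreplaced one is 0.0625/1.072 = 6%.

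**5. Chance that it arises at all.** No withdrawal rate is given. At assumed rates of 5%, 10% and 20%, the chance of at least one in-session withdrawal among 16 is 1 − (1 − p)^16 = 56%, 81% and 97%.

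**The case against.** - **The documents never say that withdrawn participants are excluded.** A reader might infer a stated exclusion, and the text does not support that. Section 7.3 says the opposite, and 7.2 offers t-tests only as an example. The omission is inferred from three facts: no planned post-baseline outcome, an analysis of change scores, and no missing-data method. The inference stands, but it is an inference.

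- **Recruitment appears to replace losses in the intervention group.** Sections 4 and 4.3.1 count intervention-group completers, and 7.1 wants 16 to complete. On that reading an active-arm loss leaves 8 completers, and the half-width stays at about 1.07 SD. This answers the precision argument for that arm. It does not remove selection bias, because a replacement is another completer and not the person lost. It also moves the data set further towards completers.

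- **Few such events are expected, and the study is a pilot.** Sections 4.4.1 and 8.5 anticipate little harm, 7.1 also cites feasibility and validating methods, and 7.2 makes hypothesis tests supportive only. All of this limits the importance of the point. Against that, estimating effect and variance is a stated purpose.

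- **Part of this is already tracked.** Retention and adherence are study outcomes (2.2.1.1, 3.3.1.1), and missing entries must be explained (9.3). These record the loss but do not recover the outcome.

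- **Attachments were not supplied.** The schedule of events, case report form, monitoring plan and consent form could bear on what is collected after withdrawal.

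**Conclusion.** The point holds as an inconsistency between 4.4.1 and 4.4.2 on one side and 7.2 and 7.3 on the other. It affects only participants withdrawn before the post-intervention visit. The likely size is modest: one loss shifts an arm mean by 0.06 to 0.19 SD without replacement, or 0.06 to 0.17 SD with it, under the assumed gap of 0.5 to 1.5 SD. If nobody is withdrawn during the sessions, the analysis is intact.

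Three stronger readings go beyond the documents:

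- That the omission would favour active stimulation. Nothing links withdrawal to arm or response, so the direction is unknown.
- That everyone who misses sessions is lost. Section 5.4 only has withdrawal considered, and those who stay in the study keep both visits.
- That each loss widens the interval. This holds only where the loss is not replaced.

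The change is worth making because it is cheap and the estimates are meant to inform a later trial. Confidence is medium, given the missing attachments and the absence of any withdrawal rate.

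**What to change.** Leave the criteria for ending sessions as they are, and reconcile 4.4.1 and 4.4.2 with 7.2 and 7.3:

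1. Record stopping sessions separately from leaving the study and from withdrawing consent.
2. Invite those who stop sessions and have not withdrawn consent to the post-intervention and 4-week assessments already planned, at times stated in the protocol and applied alike in both arms. Leave out any assessment, such as MRI, that the study physician or the existing safety screening rules out.
3. State in 7.2 that all available post-baseline data are analysed as randomised, and that participants who have been replaced still count as randomised.
4. Report by arm the numbers randomised, stopped, replaced and assessed, with reasons.

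**Cost.** A protocol amendment is needed, plus a consent amendment if the form does not already allow these visits. Each early stopper who agrees needs two to four planned visits (one or two per time point, section 3.1) at $20 each (12.2), so $40 to $80. The department bears the examination and MRI charges (12.1). Participant time is up to about 5.75 hours per time point on the stated totals (3 h + 45 min + up to 2 h of MRI). Some of the questionnaires may be done remotely under 3.2.2. No new procedure or staff is required.
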